11.1.5 Device deficiency

A device deficiency is defined as an inadequacy of the medical device under investigation with respect to its identity, quality, durability, safety, or performance.

Note 1: This includes malfunctions, use errors, and inadequate labeling.

[figure not shown]

Figure 7: Schematic representation of AE categorization

11.2 Adverse event documentation

The following information is collected:

- Name and description of the event
- Start date of the event (if applicable)
- Actions taken due to the occurrence of the event
- Outcome of the event
- Date the patient has recovered from the event
- Relationship to device or treatment under investigation
- Severity of the event
- Seriousness of the event

If detailed information regarding an AE is not available at the time of initial reporting, completion of the AE form must be achieved at the next possible point in time.

The following steps need to be taken after a study patient has experienced an SAE:

- Initial SAE report: The investigator collects as much of the following information (see SAE form) as possible for reporting to the sponsor, EC and/or competent authorities:
 - Subject demographics
 - Date of occurrence of the event
 - Description of the event, including severity and relationship to device or procedure
 - Possible cause of SAE other than the investigational device
 - Relevant medical history
 - Relevant test/laboratory data
 - Concomitant medications
 - Name and contact details of the person who has reported the event.
- The investigator completes the SAE form and follows the SAE reporting instructions according to the local applicable regulations.
- FU of the event: The investigator collects all additional information to the event (e.g. discharge summary, autopsy reports) and sends these to the sponsor, if requested. The investigator is responsible for updating the SAE form.
- Documentation: The investigator ensures that the SAE is properly documented in the patient's chart, eCRF, SAE form, and that the appropriate forms are retained in the ISF.

11.3 Serious adverse event reporting

As soon as a research team member becomes aware of an SAE, this person will ensure that the following people will be notified:

- PI
- Sponsor: For regulated studies (e.g. investigational device exemption), the sponsor will also report this information to the appropriate regulatory body.
- EC
- The investigator is obliged to submit the SAE form within 24 hours after becoming aware of the event.
- Each SAE needs to be reported by the investigator to the EC according to their regulatory requirements.
- The timelines of AE reporting are specified in the local applicable regulations.

11.4 Follow-up of adverse events

Each AE will be followed up until resolved with or without persistent damage or until the end of the patient's study participation.

All patients experiencing an AE must be monitored until the symptoms subside and any clinically relevant changes in laboratory values have returned to baseline, or until there is a satisfactory explanation for the changes observed. The results of any additional diagnostic measure (not included in the CIP) that are obtained because of the occurrence of an AE or SAE should be attached to the eCRF highlighting the date on which these measurements were taken.

For any deaths occurring during the study, a postmortem report must be supplied by the investigator to the sponsor, whenever possible.

11.5 Adverse event review

All documented AEs will be reviewed by a medical expert for completeness, medical correctness of the data and the classification into AE, SAE, ADE, SADE, U(S)ADE according to ISO 14155 definitions, as described in the SOP "Adverse Event – Documentation and Reporting" according to the "Guidelines for adverse event reporting under directives 90/385/eec and 93/42/eec".

Furthermore, the medical expert performs the review according to the process defined by the manufacturer. In case of an ADE or SADE, the manufacturer's Complaint Handling Unit needs to be informed using the AE and SAE review form provided by the manufacturer (see flowchart added below). In addition, a device report form is sent to the clinic, containing the following questions:

- Patient's demographics
- Name and contact details of the surgeon and clinic
- Device related information (e.g. decontamination, article number)
- Liability and insurance related details

The manufacturer is in charge of supporting the study site in collecting this information.

[figure not shown]

Figure 8: Adverse event review and reporting flowchart

11.6 Device deficiency reporting

The following information is collected by the investigator and reported to the sponsor:

- Specification of the deficient device
- Name and description of the deficiency
- Date of the start and resolution (occurrence) of the deficiency (if applicable)
- Actions taken due to the occurrence of the deficiency
- Consequence of the deficiency (i.e. if the deficiency may have led or led to an AE – if an AE occurred, this will be documented in the AE form)

The sponsor will analyze the information and must report only some deficiencies that could have led to a SADE. If detailed information regarding device deficiency is not available at the time of initial reporting, completion of the device deficiency form must be achieved at the next possible point in time.

11.7 Device deficiency review

In case of licensed medical device under investigation this is reported as per local law and not within the study. Additionally, if it is an investigational device, the sponsor will provide the procedures.

Furthermore, the medical expert performs the review according to the process defined by the manufacturer.

The manufacturer oversees supporting the study site in collecting this information as described in the SOP "Adverse Event – Documentation and Reporting".

12 Data management

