6.3.1.2 Regulatory status and conformity (high-level)

- The device is CE-marked; design examination certification for Activa IM-Nail is issued by DEKRA Certification B.V. (Notified Body 0344), certificate 2094913DE05.
- The manufacturer's Declaration of Conformity and applicable quality system certification references are provided as appendices.
- Continued placing on the market and putting into service under the MDR transitional provisions is documented by the manufacturer (including applicability to Activa IM-Nail and stated end of transition period for bioabsorbable implants).

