6.3.2 Comparator

The comparator device in this study is the Titanium Elastic Nail (TEN™) System (DePuy Synthes). The TEN™ system is a commercially available, CE-marked orthopedic trauma implant system used to perform elastic stable intramedullary nailing (ESIN) for stabilization of pediatric long-bone fractures, including pediatric diaphyseal forearm fractures. The TEN™ system is not investigational in the context of this clinical investigation and will be used within its approved intended use/indications and according to the manufacturer's Instructions for Use (IFU) and Surgical Technique.

The TEN™ system consists of flexible titanium alloy intramedullary nails supported by dedicated instrumentation for implantation and extraction. The nails are available in multiple diameters and lengths suitable for pediatric forearm fracture fixation (e.g., 1.5 mm × 300 mm and 2.0–4.0 mm × 440 mm).

Device traceability will be ensured by recording the device name and relevant identifiers (e.g., article number, and where applicable sterile/non-sterile designation and packaging identifiers) in source documentation and the eCRF/device accountability documentation, in accordance with local procedures. Detailed technical specifications, labeling, indications/contraindications, warnings, and handling instructions are provided in the appended TEN™ documentation (IFU/Surgical Technique/Investigator's Brochure) submitted to the Ethics Committee.

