7.2.6.6 Adverse Device Effects and Device deficiency

ADE and DD are defined in 11.1. Two cases of breakage of the Activa IM-Nail™ have been described. Steps to avoid ADE and DD have already been taken with revision of the Technique Guide. With the completion of our pilot study, we have gained valuable knowledge of the Activa IM-Nail™ procedure.

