8.3.3.1 Major protocol deviations

Major protocol deviations resulting in exclusion from the PP population will include:

- (1) implantation of a non-allocated device or cross-over to the alternate trial implant
- (2) failure to undergo intramedullary fixation after randomization
- (3) major deviations in post-operative immobilization that alter the treatment package (e.g., cast duration differing by more than ± 7 days from the planned duration, unless medically indicated and documented)
- (4) healing-related reoperation prior to reaching the radiographic healing threshold (e.g., revision fixation for loss of reduction or refracture)
- (5) missing radiographic assessments such that the healing interval cannot be determined (e.g., absence of any post-operative radiograph beyond the initial post-operative imaging or missing consecutive assessments preventing interval definition).

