19.1 Stopping rules

To identify potential safety signals or unexpected complications, an interim safety review will be performed after approximately 50% of the planned randomized participants have reached the 12-week follow-up visit (or have achieved radiographic healing, whichever occurs first).

The interim safety review will be conducted by the PI in collaboration with the sponsor and will include review of adverse events (AEs), adverse device effects (ADEs), serious adverse events (SAEs), serious adverse device effects (SADEs), and key clinical outcomes (refracture, deep infection, reoperation, loss of reduction, delayed union). If predefined stopping criteria are met, recruitment will be temporarily paused while the events are reviewed and appropriate actions are taken (including notification of the ethics committee, as applicable).

This interim review is for **safety monitoring only** (AEs/ADEs/SAEs/SADEs and prespecified healing-related safety signals including refracture and delayed healing) and is not a formal interim analysis of the primary noninferiority hypothesis; no early stopping for noninferiority/superiority efficacy is planned, and no alpha-spending adjustment will be applied based on this safety review.

Recruitment will be put on hold for safety reasons if at least one of the following incidents occurs and is assessed as possibly related to the investigational device (BIN):

- Refracture: An absolute refracture rate >25% (within the study follow-up period) will not be tolerated and will constitute a criterion for pausing recruitment.
- Delayed healing: An observed mean time to radiographic healing >12 weeks in the investigational (BIN) group will constitute a criterion for pausing recruitment.

After review, the sponsor and PI will decide whether recruitment can resume unchanged, resume with protocol modifications/risk-mitigation measures, or whether the study should be terminated.

20 Disclosures and economy

The initiative for this study has been taken solely by the authors.

The authors and affiliated colleagues have not received financial payments or other benefits from any commercial entity related to the subject of this study. The authors declare that they have no conflicts of interest.

Participants will not receive any financial compensation, gifts, or other economic benefits for participation in this study.

21 Deviations from the Clinical Investigation Plan

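### Sections 11.6 and 11.7 contradict each other on whether deficiencies of a CE-marked study nail are recorded within the study

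*Protocol*

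**What the plan says.** Protocol section 11.6 opens its list of deficiency data with "The following information is collected by the investigator and reported to the sponsor". The items cover the device, the deficiency, its dates, the actions taken and the consequence. The section requires a device deficiency form to be completed, if necessary after the first report, and sends any resulting adverse event to the AE form. It makes no exception for licensed products. On the sponsor's own duty it says that the sponsor "must report only some deficiencies that could have led to a SADE".

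Section 11.7, headed as a review section, says: "In case of licensed medical device under investigation this is reported as per local law and not within the study". Its next sentence adds that, for an investigational device, the sponsor will provide the procedures.

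Both nails are marketed products. For the BIN, section 6.3.1.2 says "The device is CE-marked; design examination certification for Activa IM-Nail is issued by DEKRA". For the TEN, section 6.3.2 says it "is a commercially available, CE-marked orthopedic trauma implant system". Appendix 3 lists both as CE-marked. Section 6.3.1 names the BIN as the investigational medical device, while 6.3.2 says that the TEN is not investigational in this study.

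Section 7.2.6.6 stands under the complications outcome, has device deficiency in its heading and notes that "ADE and DD are defined in 11.1".

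**The concern.** Site staff cannot follow both sections as written. One asks for a form and a report to the sponsor for each deficiency. The other says that for a licensed device the reporting happens outside the study. Because the nail under test is itself licensed, the exception in 11.7 covers the device the trial was set up to evaluate.

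What is at stake is the completeness of the device safety record. Implant-related complications are a secondary objective (5.2), and sections 4.6 and 9.3.2 describe fragments sheared off the BIN as a known failure of this implant. A malfunction that harms nobody is still information about the device. If 11.7 is followed literally, that kind of event may go unrecorded as a deficiency. If some staff follow 11.6 and others 11.7, or if only one nail is thought to be covered, the two arms may be recorded unevenly.

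**Working it through.** No arithmetic applies. The check sets the rules side by side and follows each kind of event through them.

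**1. Is the BIN a licensed device under investigation?** Section 6.3.1 is headed as the device under investigation and names the BIN. Section 6.3.1.2 says it is CE-marked, and 6.3.1.3 says it is used within its intended purpose. If licensed means CE-marked (the protocol does not define the word), the first sentence of 11.7 applies to it.

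**2. Does the second sentence of 11.7 cancel the first?** It also applies to the BIN, because 6.3.1 and Appendix 3 call the BIN investigational. But it is worded as an addition, does not withdraw the first sentence and states no procedure. The protocol does not say which sentence governs.

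**3. Is the TEN covered at all?** Section 11.1.5 defines a deficiency for the device under investigation, and 6.3.2 says that the TEN is not investigational. On the other hand, the intraoperative exclusion criterion in 6.1.3 speaks of investigational devices in the plural, apparently meaning both nails. The answer is unclear.

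**4. Where does each kind of deficiency end up?**

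| Event | Under 11.6 | Under 11.7, first sentence | Other route in the protocol |
|---|---|---|---|
| BIN deficiency that causes an AE | Deficiency form and AE form | Deficiency reported outside the study | Kept as AE, ADE or SADE (11.1, 11.6); reviewed under 19.1 |
| BIN deficiency without an AE | Deficiency form | Outside the study | None specific to deficiencies |
| TEN deficiency that causes an AE | AE form; deficiency form if 11.1.5 covers the TEN | Outside the study if the TEN counts as under investigation | Kept as AE |
| TEN deficiency without an AE | Deficiency form only if 11.1.5 covers the TEN | As above | None specific to deficiencies |

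**5. Would another safety route catch a harm-free malfunction?** Under 11.1.3 an adverse device effect must first be an adverse event, so it would not qualify. The interim safety review "will include review of adverse events (AEs), adverse device effects (ADEs), serious adverse events (SAEs), serious adverse device effects (SADEs), and key clinical outcomes"; deficiencies are not on that list. The monitoring focus in section 14 names device traceability and SAE/SADE reporting, not deficiencies. Surgical details are entered in the eCRF (6.2.4) and implant-specific technical details go into the restricted operative record (6.3.7.1). A failed nail may therefore leave some trace, but not as a classified deficiency.

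**Result.** Sections 11.6 and 11.7 conflict for the BIN, and coverage of the TEN is undefined. Only the two rows without an AE are exposed to loss.

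**The case against.** The strongest reply is that 11.7 concerns review and onward reporting of a marketed product, not data capture. On that reading 11.6 stands untouched, the form is still completed, and local law only decides who outside the study is told. This reading is possible, and it is why the point is a contradiction and not a proven gap. It does not remove the conflict. Section 11.6 uses the same verb for the report to the sponsor, so a rule that reporting is not within the study collides with it on plain reading.

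Four stronger readings are tempting, and the documents do not support them:

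- *That no deficiency at all would enter the trial data.* Section 11.6 still requires the form, the second sentence of 11.7 offers a sponsor route for an investigational device, and a deficiency that causes an AE goes on the AE form.
- *That the known breakages show how much would be lost.* Section 4.6 reports two sheared fragments in a study of 76 children, and both needed secondary surgery. Events of that kind would be captured as adverse events or reoperations even under the strict reading of 11.7. They say nothing about the rate of harm-free deficiencies.
- *That the primary analysis is affected.* A child whose surgeon changes implant leaves the per-protocol set because 8.3.3.1 lists "implantation of a non-allocated device or cross-over to the alternate trial implant" as a major deviation. That rule is separate from 11.7 and the correction leaves it unchanged. Replacing a BIN with another BIN does not trigger it, and the ITT analysis keeps the child in either case.
- *That the loss favours the BIN.* Both nails are CE-marked, and the documents give no comparative deficiency rate.

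It is also fair to say that the limit in 11.6 to some deficiencies concerns what the sponsor passes on after receiving the information. It loses nothing from the study data, but it gives no criterion for the choice. Adding deficiencies to the interim review in 19.1 would be a preference and is not needed to cure the contradiction.

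**Conclusion.** The point holds. Sections 11.6 and 11.7 give incompatible instructions on whether a deficiency of a CE-marked study nail is recorded within the study. The BIN meets both conditions in 11.7 with no stated priority, and it is unclear whether the TEN is covered.

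The size is limited. At risk are deficiencies that cause no adverse event, and the documents give no rate from which to estimate their number. The primary endpoint, the primary analysis and the sample size are unaffected. The conclusion rests on reading licensed as CE-marked and on taking 11.7 at its plain wording. If the sponsor meant only the external reporting route, the text still has to say so. The correction is worth making because this is a device trial and the rule, if followed, drops harm-free malfunctions of the study nails from its safety data.

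**What to change.** - In 11.7, delete the closing clause that places reporting outside the study. State that every deficiency of either study nail is recorded on the existing device deficiency form in the study database, whether or not an AE follows, in addition to any reporting required by local law. Naming both nails also settles the coverage of the TEN left open by 11.1.5 and 6.3.2.
- In 11.6, change the sponsor's duty from some to all deficiencies that could have led to a SADE.
- Tabulate deficiencies by randomised arm next to the complications. The table can be specified in the statistical analysis plan.

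The cost is a wording change in two sections, one table and a few extra form entries, including some for the TEN. The form already exists.

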12.1 Data collection, source data, storage, and archiving

Data management will be performed by the Principal Investigator (PI). Data handling and protection will be conducted in accordance with ISO 14155, ICH-GCP, and applicable national and institutional regulations.

The study complies with the EU General Data Protection Regulation (GDPR) and Danish data protection legislation (Databeskyttelsesloven and Databeskyttelsesforordningen).

The electronic case report form (eCRF) will capture all study data for each participant, as specified in this CIP. Any modification of the eCRF will be made only if necessary and in accordance with an approved amendment to the CIP.

A minimal screening log will be maintained separately from the study database, as described in Section 6.1.4.1.

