6.3.7 Blinding

Blinding is implemented to minimize performance and assessment bias [41–43]. Due to the nature of the interventions, the operating surgeon and operating room staff cannot be blinded to implant type.

Allocation is concealed from participants, parents, postoperative clinical staff, outcome assessors, and the statistician. A limited number of designated study personnel (e.g., PI and trial coordinator) are unblinded to facilitate device logistics and, when relevant, planning of elective titanium nail removal; these personnel will have no role in postoperative assessments, radiographic outcome evaluation, or data analysis.

Participant and parent unblinding will occur only after completion of the 6-month follow-up assessment, primarily to enable planning of elective removal of titanium nails in accordance with standard practice. All outcome assessors and the statistician will remain blinded until database lock and completion of the primary analysis, unless unblinding is required for patient safety.

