7.2.6.1 Re-fracture, re-displacement, or re-angulation

At each FU the radiographs are reviewed for occurrence of re-fracture, re-displacement, or re-angulation. If changes are below the boundaries described in the inclusion criteria in 6.1.1 no additional treatment is necessary. If the boundaries are exceeded the PI and the surgeon will discuss the need for additional treatment.

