8.3.2 Analysis populations

In non-inferiority trials, intention-to-treat (ITT) analyses may be biased toward non-inferiority due to treatment cross-over and non-adherence. We intend to analyze both the per-protocol (PP) and ITT populations. The primary non-inferiority analysis will be performed in the PP population. A supportive analysis will be performed in the ITT population. Non-inferiority will be considered robust if conclusions are consistent in both PP and ITT analyses. We suspect very few cases will cross over. We suspect to find similar results in both groups and a discrepancy would warrant close examination of the results.

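### Protocol 6.3.7 keeps the unblinded PI out of outcome evaluation and analysis, but 19.1 has the PI review BIN healing times mid-trial and 12.1 makes the PI data manager

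*Protocol*

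**What the plan says.** **Who is unblinded, and what they may not do.** Section 6.3.7: "A limited number of designated study personnel (e.g., PI and trial coordinator) are unblinded", and "these personnel will have no role in postoperative assessments, radiographic outcome evaluation, or data analysis".

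**What the PI does elsewhere.**
- Section 19.1: "The interim safety review will be conducted by the PI in collaboration with the sponsor". The review falls when about half of the randomized participants have reached 12 weeks or healed. It covers adverse events and key clinical outcomes, delayed union among them. One trigger for pausing recruitment is "An observed mean time to radiographic healing >12 weeks in the investigational (BIN) group".
- Section 12.1: "Data management will be performed by the Principal Investigator (PI".
- Section 7.2.6.1, for changes on follow-up films beyond the inclusion limits: "If the boundaries are exceeded the PI and the surgeon will discuss the need for additional treatment".

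**Why PP status matters.** Section 8.3.2: "The primary non-inferiority analysis will be performed in the PP population". The ITT analysis is supportive. Section 8.3.3 excludes major deviations thought likely to have a material effect on the assessment of healing. Section 8.3.3.1 lists five such deviations. They include a cast duration more than 7 days off plan, with an exception for documented medical reasons, and "healing-related reoperation prior to reaching the radiographic healing threshold".

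**Safeguards present.** Films are masked and read by two blinded reviewers, with a third to adjudicate (7.1.1.5). The statistician works on coded groups (6.3.7.4). eCRF access is role-based (12.1.2). An independent monitor checks endpoint source data and deviations (14).

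**The concern.** A reader of 6.3.7 will take it that nobody who knows the allocation touches the primary endpoint before the analysis. Sections 19.1 and 12.1 remove that assurance. By mid-trial the PI will know each child's arm and the average healing time under BIN, and will also be managing the database.

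The primary population is defined by exclusions. Most of them are plain facts, but two leave room for judgement: whether a cast deviation was medically justified, and whether a deviation matters for assessing healing. Both rest on records in a database run by an unblinded person. In a trial of 60 children, a handful of such calls could move the upper confidence limit relative to 3 weeks. The trial would also be unable to show that they were made blind.

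**Working it through.** **1. The sections side by side**

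| Activity | 6.3.7 on unblinded staff | Elsewhere |
|---|---|---|
| Radiographic outcome evaluation | No role | 19.1: PI reviews delayed union and BIN mean healing time |
| Data analysis | No role | 19.1: the pause rule needs an arm-level mean of the primary endpoint |
| Data management | Not named | 12.1: PI |
| Postoperative assessment | No role | 7.2.6.1: PI discusses further treatment after review of follow-up films |

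The clearest conflict is with 19.1. That section does not say which readings supply the BIN mean. If they are the masked readings, the PI sees primary-endpoint results by arm. If they are clinical films, healing is being evaluated outside the masked process for a review that the PI conducts. Neither fits 6.3.7. Section 12.1 defeats the purpose of the bar without breaching its wording.

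**2. The plan's own figures**

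Inputs (8.2): one-sided alpha 0.025, power 0.90, SD 3 weeks, margin 3 weeks, 10% inflation.

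- n per group = 2 × (1.960 + 1.282)² × 3² / 3² = 2 × 10.51 = 21.02, rounded up to 22. Noncentral-t power at 22 is 0.900.
- With inflation: 22 / 0.9 = 24.4, rounded up to 25.

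Both match the protocol, so no stated figure is wrong. The trial will enroll 30 per group. The interim review therefore falls at about 0.5 × 60 = 30 children, or about 15 in BIN if the arms are balanced.

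**3. Worst-case illustration**

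Assumptions: healing times are normal with SD 3; TEN mean 8 weeks; BIN mean 11, so the true delay equals the margin. The slowest k BIN children leave the PP set and no TEN child does. Non-inferiority is declared if the pooled-t upper 95% limit is below 3. Rates come from 40,000 simulated trials per setting.

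| Slowest BIN children dropped | False non-inferiority, 30 per arm | 25 per arm | Average difference, 30 per arm |
|---|---|---|---|
| 0 | 2.3% (nominal 2.5%) | 2.5% | 3.00 weeks |
| 1 | 5.0% | 5.1% | 2.78 |
| 2 | 8.1% | 8.5% | 2.61 |
| 3 | 12.2% | 12.8% | 2.44 |

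A separate run of 100,000 trials at 30 per arm gave 2.4%, 4.9%, 8.2% and 12.1%.

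**The case against.** **Data management is not data analysis.** Correct. A reader might infer that 12.1 flatly contradicts 6.3.7, but the bar does not name data management. Nothing says that the PI may edit masked readings or settles endpoint queries. Nothing rules it out either, and the role-based access in 12.1.2 is not said to do so.

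**The interim review is for safety only.** Section 19.1 says so, and a BIN-specific rule needs someone who knows the arm. It also does not say that the PI calculates the mean. This explains why the PI sees the figure. It does not make 6.3.7 accurate.

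**Reoperation decisions.** A reader might infer from 7.2.6.1 that the PI and surgeon decide on treatment and so create PP exclusions. The text says only that they discuss the need, and only healing-related reoperation before the healing threshold is excluded. Clinical care uses unedited films on which a titanium nail is visible, so clinicians may know the implant whether or not the PI is involved. The section is cited only because it has to be reconciled with 6.3.7.

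**PP classification belongs in the SAP.** Largely so. Its absence from the protocol is not the point; the point is the conflict between the protocol's own sections. Under 8.3 the SAP is due before the final analysis, so it could be written after the interim review and could not undo what was seen there.

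**Selective exclusion would be noticed.** Section 8.3.2 calls the result robust only if PP and ITT agree, and treats a discrepancy as needing close scrutiny. That is a real check. However, the primary verdict rests on PP, and agreement with ITT is not made a condition for it.

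**The error rates presuppose selective deletion.** They do. No PP rule excludes a child for healing late, and reoperated children have no observed healing time to remove. The t-interval also differs from the planned interval-censored Weibull model.

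**Conclusion.** The blinding statement in 6.3.7 is not true as written: 19.1 gives the unblinded PI an arm-level view of the primary endpoint at about half of recruitment, and 12.1 gives the PI the data. With a PP primary analysis and some judgement-based exclusions, queries and exclusions are needlessly open to handling by someone who knows the arm.

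The documents support no more than that. They neither prescribe nor foresee arm-aware exclusions. The trial's type I error cannot be said to be 5% to 12%; those rates only show how few outcome-related exclusions would matter with 30 per arm, and they assume normal times and removal of exactly the slowest BIN healers. The blinded readers and coded groups protect the scoring and the modelling. They do not cover the records and decisions that determine who is in the PP set.

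This should be corrected before enrollment, which is estimated to start in May 2026.

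**What to change.** 1. Reword 6.3.7 to state what the PI sees under 19.1 and does under 12.1, and reconcile it with 7.2.6.1. No clinical rule needs to change.
2. Use the existing role-based REDCap access so that the PI cannot edit masked-reader results or film dates.
3. State that after the interim review the PI takes no part in PP classification or in primary-endpoint queries.
4. Fix PP membership before database lock, by people blinded to arm. Raw device and cast data would reveal the arm (planned cast time is 2 weeks for TEN and 4 for BIN). They should therefore work from programmed yes/no flags: allocated device received or not, and cast duration more than 7 days from plan or not. The remaining sources are the eCRF violation records (21) and the monitoring reports (14), with arm-revealing details removed.

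Cost: protocol wording, a permission setting, two programmed flags and slightly slower data cleaning. The statistician and the monitor are already planned.
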